5.6 Supportive Care

All supportive measures consistent with optimal patient care will be given throughout the study.

5.7 Duration of Therapy

Patients will receive protocol therapy unless:

- Extraordinary Medical Circumstances: If at any time the constraints of this protocol are detrimental to the patient's health, protocol treatment should be discontinued. In this event submit forms according to the instructions in the EA6191 Forms Packet.
- Patient withdraws consent.
- Patient experiences unacceptable toxicity.
- Non-protocol therapies are administered.
- Treatment will continue until disease progression.

5.8 Duration of Follow-up

For this protocol, all patients, including those who discontinue the protocol therapy early, will be followed for response until progression, even if non-protocol-therapy is initiated. Patients will be evaluated for at least 6 months after discontinuation of study treatment and will be followed for a minimum of one year from the start of treatment, unless disease progression is reported prior to one year. One year survival information will be extracted from the medical record or by phone call for patient who have discontinued protocol treatment and completed the 6 month follow-up evaluations prior to one year from the start of treatment.

Measurement of Effect

6.1 Antitumor Effect – Solid Tumors

For the purposes of this study, patients should be re-evaluated for response every 8 (+/-1) weeks. In addition to a baseline scan, confirmatory scans should also be obtained not less than 4 weeks following initial documentation of objective response.

Response and progression will be evaluated in this study using the international criteria proposed by the revised Response Evaluation Criteria in Solid Tumors (RECIST) guideline (version 1.1) [Eur J Ca 45:228-247, 2009]. Changes in the largest diameter (unidimensional measurement) of the tumor lesions and the shortest diameter in the case of malignant lymph nodes are used in RECIST.

The following general principles must be followed:

1. To assess objective response, it is necessary to estimate the overall tumor burden at baseline to which subsequent measurements will be compared. All baseline evaluations should be performed as closely as possible to the beginning of treatment and never more than four weeks before registration.
2. Measurable disease is defined by the presence of at least one measurable lesion.
3. All measurements should be recorded in metric notation by use of a ruler or calipers.
4. The same method of assessment and the same technique must be used to characterize each identified lesion at baseline and during follow-up.

6.1.1 Definitions

Evaluable for Objective Response

Only those patients who have measurable disease present at baseline, have received at least one cycle of therapy, and have had their disease re-evaluated will be considered evaluable for response. These patients will have their response classified according to the definitions stated below.

NOTE: Patients who exhibit objective disease progression prior to the end of cycle 1 will also be considered evaluable.

Evaluable Non-Target Disease Response

Patients who have lesions present at baseline that are evaluable but do not meet the definitions of measurable disease, have received at least one cycle of therapy, and have had their disease re-evaluated will be considered evaluable for non-target lesion assessment. The response assessment is based on the presence, absence, or unequivocal progression of the lesions.

6.1.2 Disease Parameters

Measurable Disease

Measurable lesions are defined as those that can be accurately measured in at least one dimension (longest diameter to be recorded) as ≥ 20 mm by chest x-ray, as

≥ 10 mm with CT scan, or ≥ 10 mm with calipers by clinical exam. All tumor measurements must be recorded in millimeters.

NOTE: Tumor lesions that are situated in a previously irradiated area might or might not be considered measurable. If the investigator thinks it appropriate to include them, the conditions under which such lesions should be considered must be defined in the protocol.

Malignant Lymph Nodes

To be considered pathologically enlarged and measurable, a lymph node must be

≥ 15 mm in short axis when assessed by CT scan (CT scan slice thickness recommended to be no greater than 5 mm). At baseline and in follow-up, only the short axis will be measured and followed.

Non-measurable Disease

All other lesions (or sites of disease), including small lesions (longest diameter < 10 mm or pathological lymph nodes with ≥ 10 to < 15 mm short axis), are considered non-measurable disease. Bone lesions, leptomeningeal disease, ascites, pleural/pericardial effusions, lymphangitis cutis/pulmonitis, inflammatory breast disease, and abdominal masses (not followed by CT or MRI), are considered as non-measurable. Non-measurable also includes lesions that are < 20 mm by chest x-ray.

NOTE: Cystic lesions that meet the criteria for radiographically defined simple cysts should not be considered as malignant lesions (neither measurable nor non-measurable) since they are, by definition, simple cysts.

'Cystic lesions' thought to represent cystic metastases can be considered as measurable lesions, if they meet the definition of measurability described above. However, if non-cystic lesions are present in the same patient, these are preferred for selection as target lesions.

Target Lesions

All measurable lesions up to a maximum of 2 lesions per organ and 5 lesions in total, representative of all involved organs, should be identified as target lesions and recorded and measured at baseline. Target lesions should be selected on the basis of their size (lesions with the longest diameter), be representative of all involved organs, but in addition should be those that lend themselves to reproducible repeated measurements. It may be the case that, on occasion, the largest lesion does not lend itself to reproducible measurement in which circumstance the next largest lesion which can be measured reproducibly should be selected.

A sum of the diameters (longest for non-nodal lesions, short axis for nodal lesions) for all target lesions will be calculated and reported as the baseline sum diameters. If lymph nodes are to be included in the sum, then only the short axis is added into the sum. The baseline sum

of the diameters will be used as reference to further characterize any objective tumor regression in the measurable dimension of the disease.

Non-target Lesions

All other lesions (or sites of disease) including any measurable lesions over and above the 5 target lesions should be identified as non-target lesions and should also be recorded at baseline. Measurements of these lesions are not required, but the presence or absence of unequivocal progression of each should be noted throughout follow-up.

6.1.3 Methods for Evaluation of Disease

All measurements should be taken and recorded in metric notation using a ruler or calipers. All baseline evaluations should be performed as closely as possible to the beginning of treatment and never more than 4 weeks before registration.

The same method of assessment and the same technique must be used to characterize each identified and reported lesion at baseline and during follow-up. Imaging-based evaluation is preferred to evaluation by clinical examination unless the lesion(s) being followed cannot be imaged but are assessable by clinical exam.

Clinical Lesions

Clinical lesions will only be considered measurable when they are superficial (e.g., skin nodules and palpable lymph nodes) and ≥ 10 mm in diameter as assessed using calipers (e.g., skin nodules). In the case of skin lesions, documentation by color photography, including a ruler to estimate the size of the lesion, is recommended.

Conventional CT and MRI

This guideline has defined measurability of lesions on CT scan based on the assumption that CT slice thickness is 5 mm or less. If CT scans have slice thickness greater than 5 mm, the minimum size for a measurable lesion should be twice the slice thickness. MRI is also acceptable in certain situations (e.g. for body scans).

Use of MRI remains a complex issue. MRI has excellent contrast, spatial, and temporal resolution; however, there are many image acquisition variables involved in MRI which greatly impact image quality, lesion conspicuity, and measurement. Furthermore, the availability of MRI is variable globally. As with CT, if an MRI is performed, the technical specifications of the scanning sequences used should be optimized for the evaluation of the type and site of disease. Furthermore, as with CT, the modality used at follow-up must be the same as was used at baseline and the lesions should be measured/assessed on the same pulse sequence. It is beyond the scope of the RECIST guidelines to prescribe specific MRI pulse sequence parameters for all scanners, body parts, and diseases. Ideally, the same type of scanner should be used and the image acquisition protocol should be followed as closely as possible to prior

scans. Body scans should be performed with breath-hold scanning techniques, if possible.

PET-CT

At present, the low dose or attenuation correction CT portion of a combined PET-CT is not always of optimal diagnostic CT quality for use with RECIST measurements. However, if the site can document that the CT performed as part of a PET-CT is of identical diagnostic quality to a diagnostic CT (with IV and oral contrast), then the CT portion of the PET-CT can be used for RECIST measurements and can be used interchangeably with conventional CT in accurately measuring cancer lesions over time. Note, however, that the PET portion of the CT introduces additional data which may bias an investigator if it is not routinely or serially performed.

Ultrasound

Ultrasound is not useful in assessment of lesion size and should not be used as a method of measurement. Ultrasound examinations cannot be reproduced in their entirety for independent review at a later date and, because they are operator dependent, it cannot be guaranteed that the same technique and measurements will be taken from one assessment to the next. If new lesions are identified by ultrasound in the course of the study, confirmation by CT or MRI is advised. If there is concern about radiation exposure at CT, MRI may be used instead of CT in selected instances.

Endoscopy, Laparoscopy

The utilization of these techniques for objective tumor evaluation is not advised. However, such techniques may be useful to confirm complete pathological response when biopsies are obtained or to determine relapse in trials where recurrence following complete response (CR) or surgical resection is an endpoint.

Tumor Markers

Tumor markers alone cannot be used to assess response. If markers are initially above the upper normal limit, they must normalize for a patient to be considered in complete clinical response. Specific guidelines for both CA-125 response (in recurrent ovarian cancer) and PSA response (in recurrent prostate cancer) have been published [JNCI 96:487-488, 2004; J Clin Oncol 17, 3461-3467, 1999; J Clin Oncol 26:1148-1159, 2008]. In addition, the Gynecologic Cancer Intergroup has developed CA-125 progression criteria which are to be integrated with objective tumor assessment for use in first-line trials in ovarian cancer [JNCI 92:1534-1535, 2000].

Cytology, Histology

These techniques can be used to differentiate between partial responses (PR) and complete responses (CR) in rare cases (e.g., residual lesions in tumor types, such as germ cell tumors, where known residual benign tumors can remain).

The cytological confirmation of the neoplastic origin of any effusion that appears or worsens during treatment when the measurable tumor has met criteria for response or stable disease is mandatory to differentiate between response or stable disease (an effusion may be a side effect of the treatment) and progressive disease.

6.1.4 Response Criteria

6.1.4.1 Evaluation of Target Lesions

Complete Response (CR)

Disappearance of all target lesions. Any pathological lymph nodes (whether target or non-target) must have reduction in short axis to < 10 mm.

Partial Response (PR)

At least a 30% decrease in the sum of the diameters of target lesions, taking as reference the baseline sum diameters

Progressive Disease (PD)

At least a 20% increase in the sum of the diameters of target lesions, taking as reference the smallest sum on study (this includes the baseline sum if that is the smallest on study). In addition to the relative increase of 20%, the sum must also demonstrate an absolute increase of at least 5 mm.

NOTE: The appearance of one or more new lesions is also considered progression, See Section [6.1.4.3](#).

Stable Disease (SD)

Neither sufficient shrinkage to qualify for PR nor sufficient increase to qualify for PD, taking as reference the smallest sum diameters while on study. (Note: a change of 20% or more that does not increase the sum of the diameters by 5 mm or more is coded as stable disease)

To be assigned a status of stable disease, measurements must have met the stable disease criteria at least once after study entry at a minimum interval of 8 weeks.

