6.1.4.4 Evaluation of Best Overall Response

The best overall response is the best response recorded from the start of the treatment until disease progression/recurrence or non-protocol therapy (taking as reference for progressive disease the smallest measurements recorded since the treatment started). The

patient's best response assignment will depend on the achievement of both measurement and confirmation criteria.

For Patients with Measurable Disease (i.e., Target Disease)

Target Lesions	Non-Target Lesions	New Lesions*	Best Overall Response	Remarks
CR	CR	No	CR	
CR	Non-CR/Non-PD***	No	PR	
CR	Not evaluated	No	PR	
PR	Non-PD***/not evaluated	No	PR	
SD	Non-PD***/not evaluated	No	SD	Documented at least once ≥ 8 weeks from randomization
PD	Any	Yes or No	PD	No prior SD, PR or CR
Any	PD**	Yes or No	PD***	
Any	Any	Yes	PD	

* See RECIST 1.1 manuscript for further details on what is evidence of a new lesion.
 
** In exceptional circumstances, unequivocal progression in non-target lesions may be accepted as disease progression.
 
*** PD in non-target lesions should not normally trump target lesion status. It must be representative of overall disease status change, not a single lesion increase. Please refer to the Evaluation of Non-Target Lesions – Progressive Disease section for further explanation.
 
NOTE: Patients with a global deterioration of health status requiring discontinuation of treatment without objective evidence of disease progression at that time should be reported as “symptomatic deterioration.” Every effort should be made to document the objective progression even after discontinuation of treatment.
				

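### The stable-disease note in 6.1.4.1 contradicts the PR definition: a small rebound from a nadir sum below 25 mm can be coded SD while the patient is still a partial responder against baseline

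*Combined protocol and SAP*

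**What the plan says.** All the category definitions are in section 6.1.4.1.

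- **PR** is measured from baseline: "At least a 30% decrease in the sum of the diameters of target lesions, taking as reference the baseline sum diameters".
- **PD** is measured from nadir and has two parts: "At least a 20% increase in the sum of the diameters of target lesions, taking as reference the smallest sum on study", and "the sum must also demonstrate an absolute increase of at least 5 mm".
- **SD, main sentence**, is what remains: "Neither sufficient shrinkage to qualify for PR nor sufficient increase to qualify for PD, taking as reference the smallest sum diameters while on study".
- **SD, note in parentheses**: a "change of 20% or more that does not increase the sum of the diameters by 5 mm or more is coded as stable disease".

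The code on a second scan matters because of two other provisions. Section 6.1 says that "confirmatory scans should also be obtained not less than 4 weeks following initial documentation of objective response". Section 6.1.4.4 says that the "patient's best response assignment will depend on the achievement of both measurement and confirmation criteria".

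Best overall response rate by arm is secondary objective 2.2.2. Section 9.4 reports response rates by arm with 95% confidence intervals and states no test. Section 1.1 says that response is assessed by the investigator.

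**The concern.** The 5 mm clause in PD exists so that a trivial increase in a small residual tumor does not count as progression. For that purpose the note only needs to rule PD out. It goes further and assigns a category, SD, without asking whether the sum is still at least 30% below baseline. It also speaks of a *change* where an *increase* is evidently meant. One scan can then carry two codes, and no section says which prevails.

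At stake is the count of confirmed partial responses. If the scan taken to confirm a PR is coded SD because of a rebound of a few millimeters, the response may go unconfirmed. Assessment is by investigators at many sites, so the same three measurements could be recorded as PR at one site and SD at another.

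**Working it through.** The plan states no figure to reproduce here. The check applies the rules of 6.1.4.1 to example sums and then asks how often the conflict could occur.

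**1. When do the note and PR overlap?** Let *B* be the baseline sum, *n* the nadir sum and *r* the rebound, in mm. The note, read for increases, applies if *r*/*n* ≥ 0.20 and *r* < 5. Hence *n* ≤ 5*r*, and *n* must be below 25. PR still holds if *n* + *r* ≤ 0.70*B*.

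| Rebound *r* | Largest nadir that triggers the note (5*r*) | Smallest baseline at which PR still holds there (6*r*/0.70) |
|---|---|---|
| 2 mm | 10 mm | 17 mm |
| 3 mm | 15 mm | 26 mm |
| 4 mm | 20 mm | 34 mm |

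**2. Worked records (baseline, nadir, next scan).**

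| Sums, mm | From nadir | From baseline | PR definition | PD | Note |
|---|---|---|---|---|---|
| 60, 20, 24 | +20%, +4 mm | −60% | yes | no | SD |
| 100, 15, 18 | +20%, +3 mm | −82% | yes | no | SD |
| 50, 12, 15 | +25%, +3 mm | −70% | yes | no | SD |
| 20, 12, 15 | +25%, +3 mm | −25% | no | no | SD (no conflict) |
| 100, 25, 29 | +16%, +4 mm | −71% | yes | no | does not apply |

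The first three records are coded twice. The last two show the limits: once PR is truly lost, both rules give SD, and from a nadir of 25 mm a 4 mm rebound is outside the note.

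**3. How often?** The documents give neither nadir sums nor measurement error, so everything here is assumed:

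- Baseline sum lognormal, median 40, 55 or 80 mm, log-SD 0.6, floor 10 mm. For orientation, 18 of 34 patients in the earlier single-arm trial had a baseline tumor size of at least 5 cm (Table 2 of section 1.1.3).
- Residual at first PR uniform on 10% to 65% of baseline.
- No true change between scans.
- Independent multiplicative error on each sum, with coefficient of variation (CV) 5%, 10% or 15%.

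The denominator is patients at least 30% below baseline on both the first and the confirmatory scan. The last column adds a third scan with the same true sum. It counts a response as lost only if that scan also fails to show PR clear of the note.

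| CV | In the note's zone (median 80, 55, 40 mm) | Lost if one later scan may confirm (same order) |
|---|---|---|
| 5% | 0.2%, 0.3%, 0.4% | 0.03%, 0.05%, 0.06% |
| 10% | 3.8%, 5.6%, 7.0% | 1.4%, 2.1%, 2.7% |
| 15% | 6.4%, 9.7%, 12.6% | 3.0%, 4.6%, 6.0% |

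If sums truly regrow by 15% before the confirmatory scan, 12% to 24% are in the zone at CV 10%.

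**4. In patients.** In elevated LDH the earlier trial had 10/16 = 63% PR with HCQ. Table 4 of section 1.1.6 gives dabrafenib plus trametinib a best overall response rate of 50–57% and a CR rate of 8%, so about 42–49% PR. With 42 patients per arm, 42 × 0.63 + 42 × (0.42 to 0.49) = 44 to 47 partial responders. The zone then holds between 0.1 patients (44 × 0.002) and 6 patients (47 × 0.126) of 84. If a later scan may confirm, the most lost is about 3 (47 × 0.06).

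**The case against.** The strongest reply is that the note should be read in place. It is a parenthesis attached to a sentence that reserves SD for scans with too little shrinkage for PR and too little growth for PD. On that reading it explains only the PD half, and 60, 20, 24 mm remains PR. This is the better reading, and it stands to this extent: the documents do not establish that such a patient **is** scored SD, only that the text gives two answers. It does not dissolve the conflict. The note is the more specific coding instruction. The main sentence also names the smallest sum as its reference, and against that reference 24 after 20 mm is no shrinkage at all.

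Three stronger conclusions are tempting and are not supported.

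- *Every PR becomes SD.* A reader might infer this because a first shrinkage of 40% is also a change of 20% or more that adds no 5 mm. That would empty the PR category, so nobody could apply it. It shows loose drafting, not a likely harm.
- *Best response falls to SD.* Section 6.1.4.4 requires confirmation but does not say which second-scan code confirms a PR, or that only the next scan counts. Imaging continues about every 8 weeks, so a later scan may confirm. The loss is possible, not certain.
- *The HCQ effect is diluted.* A reader might infer this because the note acts on small residual tumors. No between-arm calculation supports it. Deeper response also moves patients into CR (25% against 8% in Table 4), where the PR question does not arise, so the net direction is unknown.

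It is also fair to say that the consequence is small. Under section 9.2 a PFS event is progression or death, so a PR or SD code does not touch the primary endpoint. Response rates carry no test, and with about 40 patients per arm their 95% intervals extend roughly 10 to 15 points either side.

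**Conclusion.** The contradiction within 6.1.4.1 is real and limited. A partial responder whose nadir sum is below 25 mm can be coded SD by the note after a rebound of under 5 mm while still meeting the PR definition. If that happens on the confirmatory scan, a confirmed PR can be lost. The exposure is confined to the best overall response rate.

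Its size cannot be computed from the documents. The range of about 0.2% to 13% of partial responses in the zone, and about 0.03% to 6% lost if a later scan may confirm, rests on assumed tumor sizes and no true change. It depends most on the assumed measurement error. These ranges describe what would happen if the note were followed over the PR definition; an investigator who lets the PR definition govern loses nothing. Severity is minor.

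**What to change.** Replace the note in 6.1.4.1 with:

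> An increase of 20% or more from the smallest sum on study with an absolute increase of less than 5 mm is not PD; the target-lesion assessment is PR if the sum is still at least 30% below baseline, and SD otherwise.

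Apply the same rule when response is derived from the recorded sums. The doubly coded records above then get one code, PR, and 20, 12, 15 mm stays SD.

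The cost is one sentence and the matching line in the response derivation. No scans, patients, power or alpha change. The edit does not settle which second-scan result confirms a PR; that is a separate gap in 6.1.4.4.

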6.1.4.2 Evaluation of Non-Target Lesions

Complete Response (CR)

Disappearance of all non-target lesions. All lymph nodes must be non-pathological in size (< 10 mm short axis)

Non-CR/Non-PD

Persistence of one or more non-target lesion(s).

Progressive Disease (PD)

Appearance of one or more new lesions and/or unequivocal progression of existing non-target lesions (see

Section 6.1.4.3). Unequivocal progression should not normally trump target lesion status. It must be representative of overall disease status change, not a single lesion increase.

When the patient also has measurable disease, there must be an overall level of substantial worsening in non-target disease such that, even in the presence of SD or PR in target disease, the overall tumor burden has increased sufficiently to merit discontinuation of therapy. A modest “increase” in the size of one or more non-target lesions is usually not sufficient to qualify for unequivocal progression status. The designation of overall progression solely on the basis of change in non-target disease in the face of SD or PR of target disease will therefore be extremely rare.

When the patient only has non-measurable disease, the increase in overall disease burden should be comparable in magnitude to the increase that would be required to declare PD for measurable disease: i.e., an increase in tumor burden from “trace” to “large”, an increase in nodal disease from “localized” to “widespread”, or an increase sufficient to require a change in therapy.

Although a clear progression of “non-target” lesions only is exceptional, the opinion of the treating physician should prevail in such circumstances, and the progression status should be confirmed at a later time by the review panel (or Principal Investigator).

